## 2.1.3. Exploratory Objectives

To assess the effect of pre-existing anti-dengue antibody on CD-JEV immunogenicity. Pre-existing anti-dengue antibody will be measured first by the presence of anti-dengue IgG in ELISA and secondly by anti-dengue serum neutralizing antibody titer of  $\geq 1:10$  as measured by dengue PRNT-50.

## 2.2. Study Design

This study will be a phase 4 open-label trial in which 628 Philippine infants 9 months of age will be randomized 1:1 to one of two arms:

- Group 1: 314 children receiving one dose of CD-JEV vaccine and one dose of MMR vaccine concurrently at enrollment; Group 1 will also receive a second dose of MMR per the routine immunization schedule at D84 (12 months of age).
- Group 2: 314 children receiving one dose of MMR vaccine at enrollment and one dose of CD-JEV 56 days later. Group 2 will receive a second dose of MMR per the routine immunization schedule at D84 (12 months of age).

Following receipt of study vaccine, infants will be monitored for immediate reactions during the first 30 minutes, solicited injection site and systemic adverse reactions for 14 days, unsolicited adverse events for 28 days, and serious adverse events throughout the duration of the study. All safety events will be identified or observed by study staff and/or reported by a parent. Solicited adverse reactions will be recorded by the parent on diary cards or assessed during clinic visits. Study staff will make a follow-up call to the participant's parent/guardian 2 days post vaccination (+3 days) to check on the welfare of the participant and ensure the diary card is being completed. The parent will return for a clinic visit 14 days post vaccination (+3 days) for the study staff to review the diary card, conduct safety evaluations, and review any adverse events. Information regarding unsolicited AEs will be collected during any scheduled or unscheduled clinic visit. Events will be graded for severity and assessed for relatedness to vaccination by the study clinician.

The study will be open-label; no placebo control will be employed. Due to the unequal number of injections per visit in each study arm, safety assessments will be unblinded.

Blood samples for serologic testing will be collected on Day 0, Day 28 (+7), and Day 56 (+7) for Group 1; and Day 0, Day 56 (+7), Day 84 (+7) for Group 2.

Baseline serology will be tested for antibodies to JE, measles, mumps, rubella, and dengue virus. Antibody responses to CD-JEV will be tested 28 (+7) days after vaccination, while antibody responses to the first dose of MMR will be tested 56 (+7) days after vaccination. Specifically, antibodies to measles, mumps, and rubella will be tested on Day 0 and Day 56 (+7) for both Group 1 and Group 2; antibodies to JE will be assessed on Day 0 and Day 28 (+7) for Group 1 and on Day 56 (+7) and Day 84 (+7) for Group 2; antibodies to dengue will be tested on Day 0 for Group 1 and on Day 56 (+7) for Group 2. All laboratory testing will be conducted in a blinded fashion.

Except for a screening visit which may occur on Day 0 or before, a total of 9 visits is planned for participants in Group 1 and a total of 11 visits is planned for participants in Group 2. The duration of study participation for each participant is 4 months. The duration of the study is expected to be 7 to 8 months, dependent upon the duration of enrollment period. The schedule of study visits and activities is presented in Table 1 below.

The study will be conducted at Putatan Health Center and Bayanan Health Center located within the study area of the Research Institute for Tropical Medicine, Manila, Philippines.

	Group 1									
	efore D0	D0	D2 (+3)	D14 (+3)	D28 (+7)	D56 (+7)	D84 (+7)	D86 (+3)	D98 (+3)	D112 (+7)
Obtain informed consent	x									
Collect baseline demographic information		х								
Collect/review medical history		х								
Perform physical examination		х		x	x	х	х		х	x
Check/confirm inclusion/exclusion criteria		х								
Collect serum for serology testing		х			x	х				
Administer dose of MMR		х					х			
Administer dose of CD-JEV		х								
Observe for immediate reactions for 30 minutes		х					х			
Provide diary card to parent/guardian		х					х			
Call participant to inquire about child's well-being			x					х		
Collect diary card and review reported adverse events				x					х	
Record reported adverse events		х			x	x	х			x
Record reported serious adverse events		х	x	x	x	x	х	х	х	x
Exit participant from study										х

#### Table 1. Outline of study visits and activities

#### STATISTICAL ANALYSIS PLAN

	On or b	Group 2										
	fore D0	D0	D2 (+3)	D14 (+3)	D28 (+7)	D56 (+7)	D58 (+3)	D70 (+3)	D84 (+7)	D86 (+3)	D98 (+3)	D112 (+7)
Obtain informed consent	x											
Collect baseline demographic information		х										
Collect/review medical history		х										
Perform physical examination		х		x	х	x		х	х		x	х
Check/confirm inclusion/exclusion criteria		х										
Collect serum for serology testing		х				х			х			
Administer dose of MMR		х							х			
Administer dose of CD-JEV						x						
Observe for immediate reactions for 30 minutes		х				х			х			
Provide diary card to parent/guardian		х				х			х			
Call participant to inquire about child's well-being			х				х			х		
Collect diary card and review reported adverse events				х				х			х	
Record reported adverse events		х			х	x			х			х
Record reported serious adverse events		х	x	x	х	x	x	х	х	х	x	x
Exit participant from study												х

#### 2.3. Sample Size and Power

An enrollment size of 628 participants (314 per treatment group) was targeted to achieve an overall power of 90% (approximate individual power of 95% for each coprimary objective). This estimation is based upon a non-inferiority margin of 10% and a one-sided type-one error rate of 2.5% or less, and assumes (based on historical data) a 95% seropositivity rate for measles vaccine, a 90% seropositivity rate for rubella vaccine, and approximately 20% non-evaluable rate (exclusion for baseline seropositivity and loss to follow-up) at 56 days post-vaccination. The sample size calculations were based on the Farrington-Manning score test.

#### 3. General Considerations for Data Analyses

All statistical tests except for non-inferiority will be two-sided. P-values will be recorded to 4 decimal places. All analyses will be conducted using SAS version 9.4.

#### 3.1. Analysis Set

All immunogenicity analyses and summaries will be performed on a per-protocol basis which will be considered as the primary approach to immunogenicity analyses. Supportive intention-to-treat immunogenicity analyses will also be conducted on all enrolled participants who received at least one dose of study vaccines and have at least one post-vaccination serology result. Safety analyses will be conducted on an intention-to-treat basis. In the event that there are participants who do not receive the vaccine(s) to which they were randomized, safety analyses will be performed on the safety analysis set as well. Analyses set definitions are provided below.

#### 3.1.1. Intention-to-Treat Analysis Set

The Intention-To-Treat (ITT) set will include all participants who received a study vaccine. Participants in the ITT data set will be analyzed in the group to which participants have been assigned (not based on the actual vaccine received). Participants who withdraw or are terminated from the study will be included in the ITT data set until the time of withdrawal or termination. Participants in the ITT analysis set who have at least one post-vaccination serology result will be included in the supportive immunogenicity analysis.

#### 3.1.2. Safety Analysis Set

The Safety Analysis Set (SAS) will include all participants who received a study vaccine and have at least one post-vaccination safety result. Participants in the safety data set will be analyzed based on the actual vaccine received rather than the group to which they have been randomized.

#### 3.1.3. Per-Protocol Analysis Set

The Per-Protocol (PP) sets will include the participants in the ITT set who are compliant with the protocol. This data set will be used for immunogenicity analysis only. The antigen specific PP sets are defined as follows.

## Measles Per-Protocol Analysis Set (measles-PP)

The measles-PP analysis set will be based on participants who meet all of the following criteria:

- Fulfilled the eligibility (inclusion/exclusion) criteria.
- Received all study vaccines as assigned.
- Provided a valid measles serology laboratory result at baseline and at 56 days postvaccination with MMR vaccine, with specimens taken within the windows indicated in Table 1.
- Did not take any prohibited concomitant medication within 28 days post-vaccination.
- Did not show seropositivity for measles at baseline.

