## **Statistical Analysis:** Populations for Analysis

Intent-to-Treat Analysis Set (ITT): all participants who received a study vaccine. Participants in the ITT analysis set who have at least one post-vaccination serology result will be included in the immunogenicity analysis.

Safety Analysis Set (SAS): all participants who received a study vaccine and have at least one safety measure post-vaccination. Participants in SAS will be analyzed based on the actual vaccine received rather than the group to which they have been randomized.

Measles Per-Protocol Analysis Set (measles-PP): all participants who met eligibility criteria; received all study vaccines as planned within the specified time intervals; provided valid pre- and post-vaccination serum specimens for measles within the specified time intervals; did not receive restricted medications within 28 days post vaccination; and did not show seropositivity for measles at baseline.

Mumps Per-Protocol Analysis Set (mumps-PP): all participants who met eligibility criteria; received all study vaccines as planned within the specified time intervals; provided valid pre- and post-vaccination serum specimens for mumps within the specified time intervals; did not receive restricted medications within 28 days post vaccination; and did not show seropositivity for mumps at baseline.

Rubella Per-Protocol Analysis Set (rubella-PP): all participants who met eligibility criteria; received all study vaccines as planned within the specified time intervals; provided valid pre- and post-vaccination serum specimens for rubella within the specified time intervals; did not receive restricted medications within 28 days post vaccination; and did not show seropositivity for rubella at baseline.

JE Per-Protocol Analysis Set (JE-PP): all participants who met eligibility criteria; received all study vaccines as planned within the specified time intervals; provided valid pre- and post-vaccination serum specimens for JE within the specified time intervals; did not receive restricted medications within 28 days post vaccination; and did not show seropositivity for JE at baseline.

Safety analyses will be conducted on the ITT data set. Safety analyses will also be conducted on the SAS in the event participants received vaccine(s) to which they were not randomized. Immunogenicity analyses will be based on the ITT (with at least one post-vaccination serology result), measles-PP, mumps-PP, rubella-PP, and JE-PP.

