## 4. STUDY DESIGN

This study will be a phase 4 open-label trial in which 628 Philippine infants 9 months of age will be randomized 1:1 to one of two arms:

- Group 1: 314 children receiving one dose of CD-JEV vaccine and one dose of MMR vaccine concurrently at enrollment; Group 1 will also receive a second dose of MMR per the routine immunization schedule at D84 (12 months of age).
- Group 2: 314 children receiving one dose of MMR vaccine at enrollment and one dose of CD-JEV 56 days later. Group 2 will receive a second dose of MMR per the routine immunization schedule at D84 (12 months of age).

Following receipt of study vaccine, infants will be monitored for immediate reactions during the first 30 minutes, solicited injection site and systemic adverse reactions for 14 days, unsolicited adverse events for 28 days, and serious adverse events throughout the duration of the study. All safety events will be identified or observed by study staff and/or reported by a parent. Solicited adverse reactions will be recorded by the parent on diary cards or assessed during clinic visits. Study staff will make a follow-up call to the participant's parent/guardian 2 days post vaccination (+3 days) to check on the welfare of the participant and ensure the diary card is being completed. The parent will return for a clinic visit 14 days post vaccination (+3 days) for the study staff to review the diary card, conduct safety evaluations, and review any adverse events. Information regarding unsolicited AEs will be collected during any scheduled or unscheduled clinic visit. Events will be graded for severity and assessed for relatedness to vaccination by the study clinician.

The study will be open-label; no placebo control will be employed. Due to the unequal number of injections per visit in each study arm, safety assessments will be unblinded.

Blood samples for serologic testing will be collected on Day 0, Day 28(+7), and Day 56(+7) for Group 1; and Day 0, Day 56(+7), Day 84(+7) for Group 2.

Baseline serologies will test for antibodies to JE, measles, mumps, rubella, and dengue virus. Antibody responses to CD-JEV will be tested 28(+7) days after vaccination, while antibody responses to the first dose of MMR will be tested 56(+7) days after vaccination. All laboratory testing will be conducted in a blinded fashion.

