## **5.3. Treatment Assignment Procedures**

### **5.3.1. Randomization Procedures**

This is an unblinded, individually randomized study. Enrolled children will be randomized in a 1:1 ratio to one of two arms:

- Group 1: 314 children receiving one dose of CD-JEV vaccine and one dose of MMR vaccine concurrently at enrollment;
- Group 2: 314 children receiving one dose of MMR vaccine at enrollment and one dose of CD-JEV 56 days later.

A detailed randomization standard operating procedure (SOP) will be developed and executed prior to study initiation to generate the allocation sequence. The study will use a random permuted block design to assure as close to 1:1 group balance is maintained.

PATH will maintain all electronic documents generated as part of the randomization in a secure location not accessible to other study staff involved in the trial.

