## Rubella Per-Protocol Analysis Set (rubella-PP)

The rubella-PP analysis set will be based on participants who meet all of the following criteria:

- Fulfilled the eligibility (inclusion/exclusion) criteria.
- Received all study vaccines as assigned.
- Provided a valid rubella serology laboratory result at baseline and at 56 days postvaccination with MMR vaccine, with specimens taken within the windows indicated in Table 1.
- Did not take any prohibited concomitant medication within 28 days post-vaccination.
- Did not show seropositivity for rubella at baseline.

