## JE Per-Protocol Analysis Set (JE-PP)

The JE-PP analysis set will be based on participants who meet all of the following criteria:

- Fulfilled the eligibility (inclusion/exclusion) criteria.
- Received all study vaccines as assigned.
- Provided a valid JE serology laboratory result at baseline and at 28 days postvaccination with CD-JEV vaccine, with specimens taken within the windows indicated in Table 1.
- Did not take any prohibited concomitant medication within 28 days post-vaccination.
- Did not show seropositivity for JE at baseline.

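### The per-protocol vaccine criterion has no cut-off at the endpoint blood draw, so later doses can remove valid Day 56 results from the primary analysis; the per-protocol medication window also conflicts with Protocol 6.4

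*SAP*

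**What the plan says.** SAP 3.1 makes per-protocol the main analysis: "All immunogenicity analyses and summaries will be performed on a per-protocol basis which will be considered as the primary approach to immunogenicity analyses". The intention-to-treat analysis is supportive.

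The measles, mumps and rubella sets (SAP 3.1.3; Protocol 11.2.3.1 to 11.2.3.3) share one vaccine criterion: "Received all study vaccines as assigned". The serology criterion beside it is tied to an antigen and a sample, for example "Provided a valid rubella serology laboratory result at baseline and at 56 days postvaccination with MMR vaccine". The vaccine criterion has no such tie. The Protocol Summary adds timing but still no cut-off: "received all study vaccines as planned within the specified time intervals". The JE set repeats the open vaccine criterion next to "Provided a valid JE serology laboratory result at baseline and at 28 days postvaccination with CD-JEV vaccine".

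On which doses are assigned, Protocol 5.3.1 describes Group 2 as receiving "one dose of MMR vaccine at enrollment and one dose of CD-JEV 56 days later" and does not mention a second MMR dose for either group. Protocol 4 and SAP 2.2 do list a Day 84 MMR dose in both groups, described as part of the routine schedule.

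On medication, every per-protocol set excludes prohibited medication taken in the 28 days after vaccination, without saying which vaccination. Protocol 6.4 also states per-protocol exclusions, with other windows: 14 days either side of vaccination for systemic steroids used for more than a week, and the whole study for other immunomodulating agents. Whether the whole-study window also covers immunoglobulin is unclear from the sentence.

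**The concern.** A per-protocol set should remove infants whose endpoint result does not reflect the assigned exposure. A dose given after the endpoint sample cannot change that result, so excluding on it discards valid data and selects infants on an event after the endpoint. Because per-protocol is the primary approach, this selection falls on the co-primary comparison.

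The wording also leaves membership open. An infant who has a valid Day 56 result and leaves before Day 84 is in or out depending on whether the Day 84 MMR is a study vaccine that was assigned. The trial is open-label and the statisticians are unmasked (Protocol 5.3.2), so that choice should be settled in the text and not at analysis.

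The medication rule has a similar weakness: two statements of per-protocol exclusion give different answers for the same child.

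**Working it through.** **1. Which doses follow the measles, mumps and rubella endpoint draw** (Protocol 7.3, 7.7, 7.10)

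| Dose | Group 1 | Group 2 | Can it affect the Day 56 result? |
|---|---|---|---|
| First MMR | Day 0 | Day 0 | Yes |
| CD-JEV | Day 0 | Day 56 visit, after the blood is drawn | Group 1 yes; Group 2 no, if given as scheduled |
| Second MMR | Day 84 | Day 84 | No |

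Group 2's CD-JEV is assigned on any reading, so at least one later dose is caught. It is the only later dose specific to one arm.

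**2. JE set.** If the Day 84 MMR counts, a Group 1 Day 28 JE result depends on a dose due 84 − 28 = 56 days later. In Group 2 that dose is given at the visit where the JE sample is drawn (Protocol 7.6.1, 7.10.1, 7.10.2).

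**3. The plan's own sample size.** Inputs from Protocol 11.4: margin 0.10, one-sided 0.025, rubella 90%, measles 95%, 20% non-evaluable at Day 56, Farrington-Manning score test.

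Power = Φ[(0.10 − 1.96 × SE0)/SE1], where SE0 uses the rates restricted to a difference of −0.10 and SE1 uses the assumed rates.

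- Rubella, 251 per group: restricted rates 0.8313 and 0.9313, SE0 = 0.02852, SE1 = 0.02678. (0.10 − 0.05590)/0.02678 = 1.647, power 95.0%.
- 251 is the smallest size giving 95% for rubella. 251/0.8 = 313.75, so 314 per group and 628 in total, as planned.
- Measles, 251 per group: power 99.7%.
- Joint power, assuming independence: 0.9502 × 0.9970 = 94.7%. The lower bound without that assumption is 0.9502 + 0.9970 − 1 = 94.7%, so the assumption hardly matters.

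**4. Effect of later losses on power.** The documents give no rate for missed later doses, so every loss below is an assumption. The starting point is 314 × 0.8 = 251.2 per group.

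| Assumed loss after the Day 56 draw | n, Group 1/Group 2 | Rubella power | Joint power |
|---|---|---|---|
| None (criterion cut off at the draw) | 251/251 | 95.0% | 94.7% |
| CD-JEV only, 1% of Group 2 | 251/249 | 95.0% | 94.7% |
| CD-JEV only, 2% of Group 2 | 251/246 | 94.9% | 94.6% |
| CD-JEV only, 5% of Group 2 | 251/239 | 94.7% | 94.4% |
| CD-JEV only, 10% of Group 2 | 251/226 | 94.3% | 94.0% |
| Day 84 MMR 5% in both, CD-JEV 1% of Group 2 | 239/236 | 93.9% | 93.5% |
| Day 84 MMR 10% in both, CD-JEV 2% of Group 2 | 226/222 | 92.6% | 92.0% |

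Example for the last row: 251.2 × 0.90 = 226.1 and 251.2 × 0.90 × 0.98 = 221.6. An assumed 20% loss in both arms (201/201) would be needed to bring joint power below the 90% target, to 88.3%.

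**5. Effect on the estimated rubella difference.** Suppose a fraction f of Group 2 is dropped and those infants have seropositivity pe, 10 points away from 90%. The retained Group 2 rate is (0.90 − f × pe)/(1 − f).

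| f | Retained rate, pe = 0.80 | Retained rate, pe = 1.00 | Shift in difference |
|---|---|---|---|
| 0.01 | 0.9010 | 0.8990 | ±0.1 points |
| 0.02 | 0.9020 | 0.8980 | ±0.2 points |
| 0.05 | 0.9053 | 0.8947 | ±0.5 points |
| 0.10 | 0.9111 | 0.8889 | ±1.1 points |

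If the Day 84 MMR also counts, with equal 5% or 10% loss and the same pe in both arms, most of the selection cancels. With f = 0.01 or 0.02 on top in Group 2, the shift is 0.11 to 0.23 points.

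**6. Medication windows, by example**

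- An immunomodulating agent at Day 40 precedes the Day 56 draw. It is excluded under Protocol 6.4 (whole study), but not under a 28-day rule counted from Day 0, since 40 > 28.
- A steroid course of more than a week on Days 16 to 28 lies outside the 14-day window of Protocol 6.4 but inside the 28-day rule, if such a course counts as prohibited.
- If the 28 days run from every dose, medication after Group 2's CD-JEV would remove a Day 56 result already drawn.

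**The case against.** The strongest reply is that little turns on this. For the one dose that is certainly assigned and follows the draw, CD-JEV comes minutes later at the same visit, so few infants can have a valid sample and no dose. At 1% to 2% loss, power and the estimate barely move. That stands, and it is why the effect is rated small.

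The Day 84 MMR may well not count: Protocol 5.3.1 and 5.3.2 define the arms by the first MMR and CD-JEV, and the second MMR is labelled routine. On that reading the Day 56 to Day 84 leaver and the JE example both disappear. But Protocol 4 and SAP 2.2 place the dose within the arms, so the text does not settle it.

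Protocol 11.3.1.1 frames the comparator as the two vaccines given two months apart, so requiring the whole regimen is not incoherent. Still, the objectives and SAP 6.2 compare with MMR given alone, and a dose after the draw cannot alter the result on any framing.

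The supportive intention-to-treat analysis keeps these infants, and SAP 4.2 tabulates per-protocol exclusions with reasons by group. These measures would reveal the problem but do not correct the primary set. The JE comparison is secondary with no margin, so no pass/fail decision rests on it. The steroid example depends on how prohibited is read; the Day 40 example does not share that weakness.

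**Conclusion.** The point holds on both parts. As written, the criterion removes valid co-primary results from the primary set for events after the endpoint, and it allows more than one version of that set. The per-protocol medication rule and Protocol 6.4 contradict each other.

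The size is small. Joint power stays between 94.7% and 92.0% for the losses tabulated from 1% of Group 2 up to 10% in both arms. The rubella difference shifts by about 0.1 to 0.2 points in the likelier scenarios and 1.1 points at the top of the range. The direction is unknown. These figures rest on assumed loss rates, an assumed 10-point gap in seropositivity among dropped infants, and the plan's rates of 90% and 95%. No magnitude can be given for the medication conflict, because the documents give no rate of use. The sample size itself is not in error.

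**What to change.** For the measles, mumps and rubella sets, replace the vaccine criterion with: received study vaccines as assigned, and no unassigned study vaccine, up to the Day 56 blood draw. This still excludes a Group 2 infant given CD-JEV before that draw. For the JE set, use the same wording up to the draw that follows CD-JEV. Make the Protocol Summary, Protocol 11.2.3 and SAP 3.1.3 agree.

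Separately, reconcile the per-protocol medication criterion with Protocol 6.4 so that one stated list and window applies, including for steroids and immunoglobulin. It should name the vaccination it runs from and not extend past the relevant endpoint draw. The medication reporting period in Protocol 6.4 should then match. Which agents and windows to adopt is for the study team.

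The cost is wording only, with no new visits or samples. Concomitant medications are already reviewed at clinic visits through Day 112, and SAP 5.3 summarises those collected during the study. The protocol edits need ethics approval as an amendment (Protocol 14.2, 14.3). The SAP edits can be made before database lock, by which time Protocol 11.3 requires the SAP to be final.
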